
**Enrollment:** For this pilot study, we plan to enroll 225 subjects with major depression to analyze data from 80 patients. We will ensure that subjects represent a full range of inflammation from low to high. Therefore, at least one-third of subjects will have a screening plasma CRP concentration <3 mg/L, one-third of subjects will have CRP 1-3 mg/L, and one-third subjects will have CRP >3 mg/L, measured at least twice to establish stability and rule out acute infection. Patients will be obtained from multiple referral resources including the Emory Clinic, Grady Health System, the Veterans Administration Medical Center (VAMC), and community psychiatrists. Depressed subjects will also be obtained from newspaper and radio advertisements as well as internet solicitation. We anticipate that at least 4 subjects per month will consent to enter our study. This estimate is based on ongoing projects that have been recruiting subjects for related studies over the past 5 years.

**Compensation:** Participants will be compensated using ClinCard. The ClinCard is a web-based, reloadable debit card that automates reimbursements for clinical research participants. An additional \$25 will be provided to cover travel expenses for participants that travel equal to or greater than 50 miles to Atlanta.

**Initial visit/consent signing:** After signing the consent form, subjects will complete an office intake visit(s) for further evaluation. After providing written informed consent, subjects will complete the Patient Health Questionnaire (PHQ-9) or the Quick Inventory of Depressive Symptomatology Self-Report (QIDS-SR). If eligible, subjects may undergo the initial CRP test and possibly other laboratory tests. Subjects will be compensated \$25 for this initial intake visit.

**Appointment Scheduling & Reminders:** All participants will be given the opportunity to receive appointment reminders and scheduling information via text message on their mobile phones. If the subject consents to this form of communication, study staff will only use OhMD Texting Service to communicate with participants. This platform provides a Desktop and Mobile Version of OhMD for the research team to securely communicate with participants and maintain subject confidentiality. This service will only be used for communicating relevant appointment information and never used for PHI. Participants will receive the following text message

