from the study team upon first contact: "Please do NOT send any personal information via text. You may call the study team at [REDACTED] to discuss any personal or health details." Any PHI received via text message will be reported to the IRB as a potential breach of confidentiality.

Eligibility for completing further screening and baseline assessments: The PI or PI's designee will review information collected from the initial visit to determine whether subjects are eligible to proceed with further screening and collection of baseline assessments based on the following:

- (1) Attainment of informed consent
- (2) Psychiatric clinician has determined presence of current depressive symptoms at intake with QIDS score  $\geq 14$  or PHQ-9 score  $\geq 15$ , unless otherwise approved by the principal investigator or PI's designee
- (3) The patient has not informed study staff or the psychiatric clinician of any condition that, in the opinion of the PI or PI's designee, would make the patient unsuitable for or unable to complete further screening

Medical and data quality screening criteria for LP and randomization: Subjects determined to be eligible for the study will undergo a minimum of 2 screening visits. Subjects will be compensated \$50 at each screening visit. The screening visits will include the following assessments:

- (1) Structured Clinical Interview for DSM-V (SCID)
- (2) Mini Mental State Exam (MMSE), a standard, 27-item assessment of general cognitive functioning.
- (3) Childhood Trauma Questionnaire
- (4) Bipolarity Index
- (5) Scale for the Assessment of Negative Symptoms (SANS)
- (6) Salpêtrière Retardation Rating Scale (SRRS)
- (7) Wide Reading Achievement Test (WRAT-3)
- (8) Psychiatric History Form
- (9) HDRS
- (10) SHAPS-C
- (11) MGH-ATRQ (Lifetime and Current)
- (12) Medical history and physical exam performed by a physician or nurse practitioner.
- (13) CRP (This lab is collected at least twice to establish stability – the mean will be used for group assignment. A difference of greater than 50% between values or a CRP  $\geq 10$  mg/L will warrant additional CRP sampling.)
- (14) Laboratory testing including:
  - a) an electrocardiogram
  - b) complete blood count with automated differential
  - c) comprehensive metabolic panel (with renal and hepatic function tests)
  - d) antinuclear antibodies
  - e) glycosylated hemoglobin test
  - f) thyroid stimulating hormone
  - g) tests for HIV Ag/Ab, HBV Ag, and HCV Ab,

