**Gender and Minorities:** Based on the composition of the patients treated for major depression at the Emory Clinic, Grady Health System, VAMC and community psychiatry clinics, we anticipate that an equal number of men and women will be included in the study. As for the racial composition of the sample, we anticipate 30-40% African Americans, 5-10% Latinos and 2-5% Asians, which is reflective of the community (city of Atlanta) from which our sample will be drawn.

**Dropouts:** Because participation in this study involves two screening visits followed within approximately 2 weeks by three study visits, we anticipate that there will be few subjects who will drop out between screening and the study visits. In our experience, however, there will be subjects who will have to be removed from the study because of a positive urine toxicology screen. In addition, some subjects may become too severely depressed and/or suicidal between enrollment and completion of the study. Given a conservative estimate of a 20% screen failures and 20% dropout rate, we will need to recruit ~ 225 subjects to reach the target of 80 subjects for analysis. Psychiatric staff is available throughout each subject's participation, and can provide on-site emergency care in the event of crisis.

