## **6. Participant selection**

Two hundred twenty-five depressed, medically stable males and females between the ages of 18 and 65 will be recruited for this study. All subjects (50% males and 50% females) will meet criteria for current major depression (MD). An equal number of participants will have CRP values from each of the three risk groups, as defined by CDC/AHA guidelines: <1mg/L (low), 1-3 mg/L (moderate), and >3mg/L (high). Based on retention rates in previous studies by our group utilizing a similar design in depressed subjects, we anticipate that recruiting 225 subjects will provide analyzable data for approximately 80 subjects. There will be no exclusions for race/ethnicity and minority populations and women will be actively recruited to ensure that 50% of the subjects will be female. We will make active attempts to enroll minority patients in a proportion that is reflective of the greater Atlanta metropolitan area from which patients will be recruited. No patients will be enrolled from vulnerable populations, including neonates, children, prisoners, or institutionalized individuals. No use will be made of fetal tissue. Patients will be obtained from multiple referral resources including the Emory Clinic, Grady Health System, the Veterans Administration Medical Center (VAMC), and community psychiatrists. In addition, subjects will be obtained from ongoing clinical trials including the Mental Health Centers for Intervention Development and Applied Research (CIDAR) trial, which is scheduled to enroll 400 subjects over 5 years. Depressed subjects will also be obtained from newspaper and radio advertisements as well as internet solicitation. Subjects in this study may also be referred from our Behavioral Immunology Program "Recruitment Clinic" protocol, Clinical Research in Psychiatry: IRB0000075162, which uses the screening strategy similar to this protocol to recruit and screen patients with depression for our active studies through IRB approved social media campaigns. Subjects who are determined to be eligible for this study will be referred to study staff. Participants who have consented to any Emory Behavioral Immunology Program studies will be given an option to consent to have any screening and study data used in future studies, including this study. If the participant consents to this option, any previously completed screening or study assessments may be used

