in the current study to help reduce patient burden. Some labs or evaluations may be repeated at the discretion of the PI or PI's designee, if more current data is needed. We anticipate that at least 2 subjects per month (~24 subjects per year) will consent to enter this study. This estimate is based on ongoing projects that have been recruiting subjects for related studies over the past 5 years. Of subjects who meet entry criteria, our past experience suggests that approximately 20% will discontinue study participation.

Patients with MD enrolled in the study will meet DSM-V-TR criteria for a current major depressive episode without psychosis with a symptom severity score of  $\geq 18$  on the Hamilton Depression Rating Scale (HDRS) -17 item scale. To be included, subjects must not demonstrate active suicidal intent or plan and must score  $\leq 2$  on the HDRS or QIDS suicide item, and must have no suicide attempt within six months of screening. Enrolled subjects will have no history of the following: schizophrenia, schizoaffective disorder, other (non-mood disorder) psychosis, depression secondary to a medical condition, mental retardation, and substance dependence [or abuse within the past year (except nicotine)], dementia or MMSE  $<28$ , unless otherwise approved by the PI or PI's designee, or delirium. Subjects will be at risk for exclusion for a urine toxicology screen positive for ETOH or drugs of abuse. The presence of post-traumatic stress disorder, panic disorder, obsessive compulsive disorder or social phobia will not disqualify subjects from enrollment as long as depression is the primary diagnosis, though post-traumatic stress disorder may be considered as a covariate in statistical analyses. Enrolled subjects may have a comorbid personality disorder; however, subjects who meet criteria in clinical interview for antisocial personality disorder will be disqualified, as will subjects with a history of hospitalization and/or recurrent suicidal behavior judged to be directly due to the personality disorder.

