## 7. Statistical Analysis

**Power Analysis:** To ensure a range of inflammation from low to high, we will analyze an equal number of participants from low to high inflammation levels: approximately 27 patients with CRP  $<1$ mg/L, 27 patients with CRP 1-3mg/L, and 27 patients with CRP  $>3$ mg/L. We recently completed a study using a similar enrollment strategy and analyzed data from ~80 medication-free subjects over a similar time frame. Based on our preliminary data, we anticipate large effect sizes (Cohen's dz  $\sim 1$ ) for L-DOPA-induced increases in connectivity in patients with high inflammation; thus with n=30 per group we will have  $>80\%$  power at  $\alpha=0.05$ .

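### The stated 20% screen failure and 20% dropout give 125 to 134 recruits for 80 analysable patients, not the ~225 that the protocol derives from them

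*Combined protocol and SAP*

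**What the plan says.** The derivation stands in section 5, Dropouts: "20% screen failures and 20% dropout rate, we will need to recruit ~ 225 subjects to reach the target of 80 subjects for analysis". The same sentence calls the estimate conservative. Just before it, the paragraph expects few dropouts between screening and the study visits. It also foresees removals for positive urine toxicology and losses from worsening depression or suicidality, without a rate for either.

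The pair 225 and 80 appears in two other places. Section 5, Enrollment: "we plan to enroll 225 subjects with major depression to analyze data from 80 patients". Section 6: "recruiting 225 subjects will provide analyzable data for approximately 80 subjects", based there on retention in the group's earlier studies, with no rate. Section 6 then gives the one rate attributed to past experience: "Of subjects who meet entry criteria, our past experience suggests that approximately 20% will discontinue study participation".

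Two design features bear on losses but do not enter the derivation.

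- **Intake after consent.** Section 5 says "After signing the consent form, subjects will complete an office intake visit(s) for further evaluation". One condition for going on to screening is "Psychiatric clinician has determined presence of current depressive symptoms at intake with QIDS score" of at least 14, or a PHQ-9 score of at least 15.
- **Equal CRP strata.** Section 6 says "An equal number of participants will have CRP values from each of the three risk groups", and section 7 says "we will analyze an equal number of participants from low to high inflammation levels", with about 27 patients in each of three strata.

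**The concern.** The Dropouts sentence gives a premise (two loss rates) and a conclusion (about 225 recruits), and the two are far apart. This is the only numerical derivation of the enrolment figure in the protocol.

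Two explanations are possible, and they have different consequences. If the true expectation is 80 analysable from 225, the stated rates are too low or a loss was left out. Attrition that is on plan would then look like failure when set against 20% and 20%. If the rates are right, the study would consent many more people than it needs. These are patients with untreated major depression, followed for up to four weeks (section 9). The text does not let a reader tell which applies.

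**Working it through.** **Inputs**

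- Screen failure 20% and dropout 20%: section 5, Dropouts.
- Denominator of the dropout rate, subjects who meet entry criteria: section 6. Dropout therefore follows screening, and the losses are sequential.
- Analysable target 80: section 5, Enrollment and Dropouts; section 6. Section 7 gives 3 × 27 = 81, and its power statement uses 30 per group, or 3 × 30 = 90.
- Stated recruitment: ~225.

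**Step 1. Try to reproduce 225**

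Recruits needed = target / proportion retained.

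| Target | Sequential, retained 0.8 × 0.8 = 0.64 | Additive, retained 1 − 0.40 = 0.60 |
|---|---|---|
| 80 | 125 | 133.3, so 134 |
| 81 | 126.6, so 127 | 135 |
| 90 | 140.6, so 141 | 150 |

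Inflating by multiplication, a common mistake, gives less: 80 × 1.2 × 1.2 = 115.2 and 80 × 1.4 = 112. Three, four or five successive 20% losses give 80/0.8³ = 157, 80/0.8⁴ = 196 and 80/0.8⁵ = 245 (rounded up). None of these is 225. The gap is 225 − 125 = 100 recruits, or 225 − 134 = 91, too large for rounding or for the approximation sign.

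Dividing by the fraction lost instead of the fraction retained comes close: 80/0.36 = 222 and 81/0.36 = 225. That may be how the figure arose, but this is conjecture and would not validate it.

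**Step 2. Run the stated rates forward from 225**

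- Sequential: 225 × 0.8 = 180 pass screening; 180 × 0.8 = 144 analysable.
- Additive: 225 × 0.60 = 135 analysable.

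**Step 3. Size of the loss without a rate**

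- Total loss implied: 1 − 80/225 = 64.4%. The stated rates account for 36% (sequential) or 40% (additive).
- Further loss needed after both stated losses: 1 − 80/144 = 44.4% (sequential) or 1 − 80/135 = 40.7% (additive).
- Put another way, with 20% discontinuation kept as in section 6, 80 analysable needs 80/0.8 = 100 entrants. Then 125 of 225, or 55.6%, must be lost before entry, against a stated screen failure of 20%.

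**Step 4. Look for the missing rate elsewhere**

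Section 5, Enrollment, repeats 225 and 80 without a rate. Section 6 refers to earlier retention without a figure, and its one figure is the same 20%. Section 7 mentions a recent study with a similar enrolment strategy and about 80 analysed, but not how many it recruited. No section supplies a rate that brings total loss to 64%.

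**The case against.** The strongest reply is that 225 does not rest on the Dropouts sentence alone. Section 6 bases it on retention in the group's earlier studies of similar design, and the recent study in section 7 is relevant experience. Several real losses lie outside a narrow 20% and 20%: failure at intake after consent, toxicology removals, clinical worsening, terminated or unusable scans, and surplus patients once a CRP stratum is full. The target of about 80 is consistent, the study calls itself a pilot, and any error runs towards recruiting too many.

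Much of this stands, and it rules out stronger conclusions that a reader might draw.

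- **That 225 is too high and should become 125.** The documents do not support this. Equal strata alone could require more than 125. Suppose 27 completers per stratum, the stated rates, and a rarest stratum holding one third, 30%, 25% or 20% of recruits. Then 27/(share × 0.64) gives about 127, 141, 169 or 211 recruits. These shares are assumptions; the protocol gives none. Section 6 also allows referral from a separate recruitment protocol and reuse of earlier screening data, so surplus patients might never count as enrolled here.
- **That recruitment cannot be monitored.** The totals and stratum targets are explicit, and section 9 has the DSMB review numbers consented, randomised and dropped out, with reasons. Only the stage-specific loss rates cannot be checked.
- **That the error settles the study's duration.** The two accrual rates, 4 per month in section 5 and 2 per month in section 6, conflict whatever recruitment number is used. That is a separate point.

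What does not stand is the idea that the possible extra losses rescue the derivation. None has a rate, and the protocol does not say whether any is included in the 20% and 20%.

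**Conclusion.** The derivation is wrong or incomplete as written. At the stated rates, 80 analysable patients need 125 recruits if the losses are sequential, or 134 if they are added. The sequential reading is the better supported, because section 6 applies discontinuation to those who meet entry criteria. The plan's figure exceeds these by 100 or 91, and a further loss of about 44% or 41% has no stated rate. This rests only on the protocol's own rates and target, and alternative targets of 81 or 90 do not change it.

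Whether 225 is the right number cannot be decided from the documents. A reader might also infer a loss of power. There is none: power depends on the number analysed, and at the planned dz of 1 a two-sided paired t test at 0.05 has 99.88% power with 27 patients and 99.96% with 30. The point should be fixed because 225 is the headline enrolment figure and the correction is cheap.

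**What to change.** In section 5, Dropouts, restate the loss rates by stage from the group's own intake, screening and retention data, so that the product gives the stated recruitment number. Say for each of these whether it is counted, and in which stage:

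- failure at intake after consent;
- screen failure;
- toxicology removals;
- clinical worsening;
- other dropout;
- terminated or unusable scans;
- surplus patients in filled CRP strata.

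Keep 225 if the product supports it. Otherwise restate the recruitment number. Either way, make section 5, Enrollment, and section 6 agree, including the 20% discontinuation rate.

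Separately, and minor: reconcile the accrual rates (4 per month in section 5, 2 per month in section 6) and the group size in section 7 (27 against n=30). The claim of more than 80% power holds at either size.

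The cost is a text change and a look-up of rates from earlier studies. The analysis does not change, and the recruitment number changes only if those data require it.

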## **Study Procedures**

### **Neuropsychiatric Assessments:**

#### **Observer-rated assessments**

**Mini Mental State Exam** is an 11 question tool that assesses mental status. The questions cover five areas of cognitive functioning.

**Hamilton Depression Rating Scale (HDRS):** The-HDRS is a 24-item, clinician-administered scale that rates severity of depression.

**Scale for the Assessment of Negative Symptoms (SANS):** The SANS is a 25-item, clinician-administered scale that rates the severity of negative psychiatric symptoms including affective flattening, poor attention, and anhedonia.

#### **Structured Clinical Interview for DSM-VIV (SCID-Modified):**

**Mood modules-** These modules from the SCID will allow for a categorical diagnosis of the presence or absence of major depression or other DSM-VIV mood disorder. Such categorical diagnoses will complement symptom severity ratings offered by the HDRS.

**Alcohol and Drug Abuse/Dependence Module:** These SCID sections allow for assessment for current or past presence of alcohol and drug abuse/dependence.

**Eating Disorder and Anxiety modules:** These sections allow for a diagnosis of the presence or absence of eating disorders and anxiety disorders.

**Psychotic module:** This module from the SCID will allow for the assessment of the presence or absence of psychotic symptoms.

**Salpetriere Retardation Rating Scale (SRRS):** The SRRS is a 15-item, clinician-administered scale to assess clinical psychomotor retardation (71). The 15 items of the scale are either related to motility or mental activity.

**Psychiatric History:** This form assesses the psychiatric history of the subject.

**WRAT-3:** The WRAT-3 is a very brief screening measure for reading level.

**Bipolarity Index:** The bipolarity index assesses five symptom dimensions that are characteristic of patients with bipolar disorder. The degree of severity of each dimension is calculated.

**Snaith-Hamilton Pleasure Scale (SHAPS-C):** Clinician administered assessment of anhedonia.

**Hamilton Anxiety Rating Scale (HAM-A):** The HAM-A is a 14-item clinician-administered scale that assesses the severity of symptoms of anxiety.

**Self-report questionnaires :**

**Lifetime and Current Massachusetts General Hospital Antidepressant Treatment Response Questionnaire (MGH-ATRQ):**

The MGH-ATRQ is a measure of treatment resistance that uses a simple numbering system to quantify both the number of failed antidepressant treatment trials as well as the intensity/optimization of each trial (72). Unlike other resistance classification schema, the MGH-ATRQ does not make assumptions regarding a hierarchy of antidepressant classes (72, 73). The MGH-ATRQ generates a continuous variable reflecting the degree of resistance in depression, with higher scores indicating a greater likelihood of non-response (73).

**State-Trait Anxiety Inventory (STAI) State Scale:** This 20-item self-report scale is used to measure current anxiety symptoms.

**Demographic Questionnaire:** This form is used to capture basic demographic information of each subject.

**Patient Health Questionnaire (PHQ-9):** is a nine-item measurement used to assess depressive symptoms and suicidal ideation.

**Quick Inventory of Depressive Symptoms (QIDS):** is a 16 item clinician-assisted self-report instrument that include assessment of nine diagnostic symptom domains used to characterize a major depressive episode.

**Inventory of Depressive Symptoms-Self Report (IDS-SR):** is a 30-item self-report instrument with excellent psychometric properties that was designed to measure symptom constructs including psychomotor retardation, fatigue and anhedonia consistent with current DSM nosology (74, 75).

**Multidimensional Fatigue Inventory (MFI)** To evaluate the presence and severity of fatigue, subjects will complete the self-report, 20-item Multidimensional Fatigue Inventory (MFI-20)(76). Consistent with recent data regarding the structure of fatigue in medically ill patients (77), the MFI assesses 5 dimensions of fatigue, including general fatigue, physical fatigue, mental fatigue, reduced activity and reduced motivation. In addition to scores for each subscale, a total score can be derived by summing the 5-subscale scores (78).

**Epworth Sleepiness Scale (ESS)** will be used to assess subjective sense of daytime alertness (79). The ESS is a widely used measure of self-reported alertness. The ESS is a 24 point scale, with 8 different items for which the patient rates the likelihood of falling asleep on a 0-3 scale. Higher scores signify a greater likelihood of daytime sleepiness. The ESS has been reported to distinguish conditions characterized by excessive daytime sleepiness (i.e., narcolepsy, sleep apnea) from control populations (79).

**Pittsburgh Sleep Quality Index (PSQI)** will be used to assess sleep quality over the past month and can be used to distinguish good sleepers from bad sleepers (80). The scale contains 15 multiple-choice items that inquire about frequency of sleep disturbances and subjective sleep quality and 4 write-in items that inquire about typical bedtime, wake-up time, sleep latency, and sleep duration. The PSQI generates seven scores that correspond to relevant domains of sleep, and each score ranges from 0 (no difficulty) to 3 (severe difficulty). The component scores are summed to produce a global score (range of 0-21). A PSQI global score >5 is considered to be suggestive of significant sleep disturbance (80).

**Snaith-Hamilton Pleasure Scale (SHAPS)** is a 14-item scale used to assess present-state hedonic tone (81). The items 1, 4, 8 and 9 refer to interests, items 3 and 10 to food and drink, items 2, 7, 13 and 14 to social interaction and items 5, 6, 11 and 12 to sensory experiences.

**Childhood Trauma Questionnaire (CTQ):** The CTQ is a self-report inventory assessing 3 types of childhood abuse: sexual, physical, and emotional. Studies have established the internal consistency, stability over time, and criterion validity of both the original 70-item CTQ and the current brief version (82). The CTQ yields a total score and subscale scores for each of the types of child abuse. CTQ data from Emory have demonstrated good internal consistency reliability (alpha = .99 for physical abuse; alpha = .94 for sexual abuse; alpha = .93 for emotional abuse; and alpha = .98 for the total of these 3 scales). The data from the CTQ will be used to classify subjects into 2 categories for each type of abuse (physical, sexual, and emotional): (1) those with CTQ scale scores in the none to mild range, and (2) those with CTQ scores in the moderate to severe range. We will then create a composite variable across all of the 3 types of abuse. Using this composite, we can divide participants into 2 groups with respect to the numbers of types of abuse that fall into the moderate to severe

range: (1) those with no type of abuse in the moderate to severe range, and (2) those with at least 1 type of abuse in the moderate to severe range (83).

**Habits:** The Habits form is a brief questionnaire that assesses a subject's daily smoking, daily caffeine consumption, and exercise patterns.

**Beck Depression Inventory, 2nd edition (BDI-II), Anhedonia Subscale** is a subscale of the 21-item self-report measure of depressive symptoms, rated on a 4-point Likert scale based on the patient's experience in the last two weeks.

**Profile of Mood States (POMS)** is a psychological rating scale used to assess transient, distinct mood states. Participants rate the extent to which they feel: unhappy, blue, lonely, gloomy, and worthless on a scale from 0 (not at all) to 4 (extremely).

**Post-traumatic Stress Disorder Symptom Scale (PSS):** The PSS is a 17-item self-report scale that assesses the presence and severity of symptoms related to a single identified traumatic event in individuals with a known trauma history.

**Perceived Stress Scale** is a self-report scale measuring the perception of stress. The items are designed to predict how uncontrollable, unpredictable, and overloaded the subjects find their lives.

**Visual Analog Scale of Pain:** is a scale between the range of 1 to 10, that measures the perception of pain.

**Staging System for Reproductive Aging and Menopause Rating Scale (MRS)** is an 11-item self-report scale that assesses the presence and severity of symptoms related to menopause including psychiatric and physical symptoms. This form will be administered to female subjects only.

**Columbia-Suicide Severity Scale:** The Columbia-Suicide Severity Rating Scale (C-SSRS) is a fully-structured, clinical interview designed to systematically query patients regarding past and current suicidal ideation and behavior (SIB) (100). The psychometric characteristics of the patient- reported C-SSRS have been assessed in multiple contexts. It has well validated to elicit suicidal ideas in depressed subjects and will be consequently used to identify individuals experience acute severe depressive symptoms and refer them for immediate treatment.

**Post-Traumatic Stress Disorder Checklist for DSM-5 (PCL-5):** The PCL-5 is a 20-item self-report measure that assesses the 20 DSM-5 symptoms of PTSD, rated on a 5-point Likert scale based on the patient's experience in the last month.

**Beck Anxiety Inventory (BAI):** The BAI is a 21-item self-report measure of anxiety symptoms, rated on a 4-point Likert scale based on the patient's experience in the last month.

**Motivation and Pleasure Scale (MAP):** The motivation and pleasure questionnaire is an 18-item self-report inventory that was created to disentangle state-wise motivational and consummatory components of everyday activities over a 24-hour period, and has been previously validated as a measure of reward-related symptoms in psychiatric populations. This scale will be used to assess self-reported changes in symptoms of anhedonia before and after inflammation blockade.

